6.3.2 Dose Proportionality (for SAD only)

An assessment of dose proportionality will not be based strictly on statistical criteria, but rather several factors will be considered when assessing dose proportionality, such as results derived from a Power Model (Gough et al, 1995) (e.g., the slope estimate, and the width of the 90% confidence interval [CI]) and descriptive statistics.

Details are as follows:

Power Model: The power model will be used to estimate the slope parameter and its 90% CI. The general form of the power model is described as:

$$\ln(\text{PK Parameters}) = \beta_0 + \beta_1 \ln(\text{Dose}) + \varepsilon$$

This approach is usually referred to as a power model because after exponentiation:

$$PK \text{ Parameters} = \alpha Dose^{\beta_1}$$

where α only depends on the β_0 , ϵ and represents the intercept of the line and β_1 represents the slope of the line.

Dependent Variables (PK Parameters):

- C_{max}, AUC_{0-t}

Independent Variables:

- The regression above is a univariable regression. The only independent variable in this model is natural logarithm transformation of dose level (e.g., ln(dose)). No other covariates will be controlled for.

Dose proportionality can generally be concluded if the 90% CIs around the slope estimate (i.e., β_1) include the value of 1.

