5.3.2. Part A Dosing

Study drug will be administered once on Day 1. Part A dosing will commence with 2 sentinel subjects prior to dosing the remainder of each cohort (refer to [Section 5.3.1](#)).

Study drug will be administered in the morning together with a glass of tap water under a fasted state, i.e., after an overnight fast of at least 10 hours and no food is allowed for at least 2 hours after drug administration. Please refer to [Section 5.10.3](#) for information related to fluid and food restrictions both pre- and postdose.

[Table 3](#) provides the planned dose-escalation schedule. Of note, dose escalations will not exceed dose-doubling in principle.

Table 3 Planned Dose-Escalation Schedule (SAD Part A)

Cohort	Oral Daily Dose (mg/day) ¹		Total Number of Capsules (Number - Strength) ¹	
	KNX100	Placebo	KNX100	Placebo ²
1	5	0	1 capsule (1 × 5 mg)	1 capsule (1 × 0 mg)
2	15	0	3 capsules (3 × 5 mg)	3 capsules (3 × 0 mg)
3	25	0	25 mg: 1 capsule (1 × 25 mg)	25 mg: 1 capsule (1 × 0 mg)
4	50	0	50 mg: 2 capsules (2 × 25 mg)	50 mg: 2 capsules (2 × 0 mg)

Abbreviations: PK = pharmacokinetics.

¹ All dose levels beyond Cohort 1 may change based on emerging safety and PK data.

² An equivalent number of capsules will be administered to subjects receiving placebo.

*Additional cohorts may be added as required, based on safety profile and CRC authorization.

Dose escalation and de-escalation will follow the processes outlined in [Section 5.3.4](#).

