5.3.4. Dose Escalation

An evaluable subject is one that has been dosed, completed all assessments, and had their data reviewed by the CRC.

Blinded data to be reviewed by the CRC for each subject will include (as a minimum): PK (up to 30 hours postdose for Part A and 24 hours postdose for Part B), EEG, ECG, vital signs, pulse oximetry, neurological examination, and any adverse events.

The CRC may approve dose escalation following review of cohort data if:

- No drug related SAE's occurring within 48 hours of administration of KNX100 or placebo is observed in any subject in the dose group under evaluation.
- No drug related AE's of Grade 3 or greater are observed in 2 or more subjects within a dose group.
- The mean KNX100 C_{max} **OR** AUC does not exceed 84.9 ng/mL or 82.7 ng×h/mL respectively **and** the mean KNX100A C_{max} **OR** AUC does not exceed 26.5 ng/mL and 45.7 hr × ng/mL, respectively, the exposure associated with 1/10th of the NOEL of 2.75 mg/kg observed in the 14-day dog EEG study.
- No emergence or evidence of other PI-deemed and or medical monitor-deemed clinically significant abnormal vital signs, neurological and physical examination, or safety parameters postdose have been observed.

Dose increases will be permitted once review of data from all evaluable subjects has been performed.

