8.2. Determination of Sample Size

This study is descriptive in nature, and no formal comparisons or hypothesis testing will be performed between study medications or dosing levels. As such, no prospective calculations of statistical power have been made. The sample size has been selected to provide sufficient information to have preliminary characterization of safety, tolerability, PK and PD of the study drug.

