Residual area	Percentage of AUC _{0-∞} due to extrapolation from the time of last non-zero concentration to infinity.
DN AUC	Dose-normalized AUC, calculated as AUC/ Dose where AUC is AUC ₀₋₈ and AUC _{0-last}
DN C _{max}	Dose-normalized C _{max} , calculated as C _{max} / Dose

MAD

Parameter (Unit)	Method
C _{max} (ng/mL)	Maximum plasma concentration obtained directly from the observed concentration versus time data, Day 1 and Day 7
AUC _{0-∞} (h*ng/mL)	Area under the plasma concentration-time curve from time zero (pre-dose) extrapolated to infinity (units) calculated by linear trapezoidal rule and extrapolated to infinity by the addition of the last quantifiable concentration divided by the terminal rate constant: AUC _{0-last} + C _{last} /λ _z . Day 7 only
AUC _{0-last} (h*ng/mL)	Area under the plasma concentration-time curve from time zero to the time of the last quantifiable concentration at time "t" (units), over the whole plasma profile on Days 1 and 7, calculated by linear trapezoidal rule. Cohorts 1, 2 and 3
AUC _{0-8h} (h*ng/mL)	Area under the plasma concentration-time curve from time zero to 8 hours after dosing, calculated by linear trapezoidal rule. Days 1 and 7, Cohorts 1, 2 and 3
AUC _{8-16h} (h*ng/mL)	Area under the plasma concentration-time curve from time 8 hours to 16 h after first dose, calculated by linear trapezoidal rule. Days 1 and 7, Cohort 3
T _{max} (h)	Time to maximum plasma concentration obtained directly from the observed concentration versus time data. Day 1 and Day 7
CL/F _{ss} (L/h)	Plasma clearance estimated as dose divided by AUC _{0-tau} . Day 7 only where data permits
V _z /F (L)	volume of distribution estimated by dividing the apparent clearance by λ _z . Day 7 only
λ _z (h ⁻¹)	Apparent terminal elimination rate constant estimated by log-linear least-squared regression of the terminal part of the concentration-time curve profile. Day 7 only
t _{1/2} (h)	Elimination half-life, calculated as ln(2)/λ _z . Day 7 only
Residual area	Percentage of AUC _{0-∞} due to extrapolation from the time of last non-zero concentration to infinity. Day 7 only
RA AUC	Accumulation Ratio for AUC, calculated as AUC _{Day 7} / AUC _{Day 1} , Cohorts 1, 2 and 3 (note the time interval over which the AUC will be determined will be dependent on the quantifiable data).

Parameter (Unit)	Method
RA Cmax	Accumulation Ratio for Cmax, calculated as Cmax Day 7 / Cmax Day 1

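### The only stated criterion for concluding dose proportionality in SAP 6.3.2, a 90% CI for the slope that includes 1, is non-rejection, and a wide CI meets it more easily

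*SAP*

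**What the plan says.** SAP section 6.3.2 applies to Part A (SAD) only. It regresses the log of Cmax and of AUC0-t on log dose, with no other covariate, and estimates the slope β1 with a 90% CI.

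The section opens cautiously: "An assessment of dose proportionality will not be based strictly on statistical criteria". Among the factors to be weighed it gives "the slope estimate, and the width of the 90% confidence interval", together with descriptive statistics. It closes with a criterion: "Dose proportionality can generally be concluded if the 90% CIs around the slope estimate", β1, "include the value of 1".

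Neither document gives acceptance limits around 1, a maximum CI width, or a rule for an imprecise interval. Table 4 in SAP section 6.3.1 also plans dose-normalised exposure for Part A ("Dose-normalized AUC, calculated as AUC/ Dose", and the same for Cmax). Protocol section 8.2 sets the general frame: "This study is descriptive in nature, and no formal comparisons or hypothesis testing will be performed between study medications or dosing levels".

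**The concern.** A 90% CI for β1 that includes 1 is equivalent to failing to reject β1 = 1 in a two-sided 10% test. A small or noisy data set fails to reject almost anything, so the criterion favours poor precision. It also errs the other way. A CI of 1.02 to 1.08 would fail, although over a 10-fold dose range it implies a departure of only 10^0.02 = 1.05-fold to 10^0.08 = 1.20-fold.

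What is at stake is the wording of the report. A reader told that proportionality was concluded would take exposure at other doses to be predictable by simple scaling, when the data may not support that. A departure is not far-fetched. Protocol section 3.2.1 mentions a tendency in the nonclinical data for exposure to rise faster than dose, and section 1.2 says oral bioavailability appeared to rise with dose in animals. Neither shows what happens in humans, but both argue against a criterion that can pass for lack of information.

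**Working it through.** The documents state no power or precision figure for this analysis, so there is none to reproduce. The check asks how often the closing criterion would be met when exposure is truly not proportional.

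**Inputs from the documents**
- Planned doses 5, 15, 25 and 50 mg (Protocol section 5.3.2, Table 3), so the dose ratio is r = 50/5 = 10.
- 6 active subjects per cohort (Protocol section 5.2), so N = 4 × 6 = 24 and df = 22.
- Simple regression on ln(dose) with a 90% CI (SAP section 6.3.2), so t(0.95, 22) = 1.717.

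**Assumed inputs**
- Between-subject CV of 20, 30, 50, 70 or 100%. Neither document gives one.
- Log-normal error with constant variance, and an evaluable parameter from all 24 active subjects.
- True slopes of 1.2 and 1.3 as illustrations. The documents do not say what size of departure matters.

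**Formulas**
- σ = √ln(1 + CV²).
- Sxx = 6 × Σ(ln dose − mean)². The log doses are 1.609, 2.708, 3.219 and 3.912, with mean 2.862, so Sxx = 6 × 2.8225 = 16.94.
- SE = σ/√Sxx, and the approximate CI half-width is 1.717 × SE.
- Fold-departure in dose-normalised exposure over the range = r^(β1 − 1). This is 10^0.2 = 1.58 for slope 1.2 and 10^0.3 = 2.0 for slope 1.3.
- P(CI includes 1) = F(1.717; 22, δ) − F(−1.717; 22, δ), where F is the noncentral t distribution function and δ = (β1 − 1)/SE.

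**Results**

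| CV | σ | SE | Half-width | P, slope 1.0 | P, slope 1.2 | P, slope 1.3 |
|---|---|---|---|---|---|---|
| 20% | 0.198 | 0.048 | 0.083 | 90% | 0.9% | 0.0% |
| 30% | 0.294 | 0.071 | 0.122 | 90% | 14% | 0.8% |
| 50% | 0.472 | 0.115 | 0.197 | 90% | 48% | 19% |
| 70% | 0.631 | 0.153 | 0.263 | 90% | 65% | 40% |
| 100% | 0.833 | 0.202 | 0.347 | 90% | 75% | 58% |

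Slopes of 0.8 and 0.7 give the same probabilities by symmetry. A simulation of 400,000 trials per cell agreed within 0.2 percentage points. Under exact proportionality the criterion is met 90% of the time whatever the CV, so meeting it says nothing about precision.

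**What a pass can hide.** Suppose the estimated slope is exactly 1. The 90% CI for the fold-departure runs from 10^(−half-width) to 10^(half-width): 0.83–1.21, 0.75–1.33, 0.64–1.57, 0.55–1.83 and 0.45–2.23 across the five CVs. All five meet the criterion, yet the last is also compatible with a two-fold departure in either direction.

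**A narrower dose range.** Table 3 carries the note "All dose levels beyond Cohort 1 may change based on emerging safety and PK data". With 5, 15 and 25 mg only (N = 18, Sxx = 8.12, r = 5), a true slope of 1.25 (5^0.25 = 1.50-fold) meets the criterion 25% of the time at CV 30% and 58% at CV 50%. With 5, 15, 25 and 35 mg (N = 24, Sxx = 13.01, r = 7), a slope of 1.2 (7^0.2 = 1.48-fold) meets it 23% and 56% of the time, against 14% and 48% for the planned set.

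**The case against.** The strongest reply is that the section already contains its own safeguard. It disclaims a strictly statistical assessment, lists CI width and descriptive statistics as factors, and softens the closing sentence with a qualifier. Nobody is obliged to declare proportionality from a wide interval. The slope, its CI and the dose-normalised parameters are all planned, so a careful reader could see the imprecision. The large probabilities need a CV of 50% or more, which the documents do not support; at CV 20% the two departures almost never pass.

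The consequence is also small. Proportionality is not among the objectives or endpoints (SAP section 2, Protocol section 8.5.2). The escalation criteria in Protocol section 5.3.4 compare mean exposure with fixed caps, "the exposure associated with 1/10th of the NOEL of 2.75 mg/kg observed in the 14-day dog EEG study", and do not use the power model.

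Most of this stands, and it sets the weight of the point. The probabilities above are for meeting one sentence, not for the report's overall judgement. But naming CI width without saying how it counts does not correct the closing sentence, which is the only place the section says when a conclusion may be drawn. The qualifier softens that criterion without changing its logic. If judgement is meant to govern, the sentence is unnecessary. The descriptive character of the study points the same way: an estimate with its CI is descriptive, whereas a conclusion drawn from whether the CI includes 1 is a hypothesis test in effect.

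**Conclusion.** The concern holds. The closing sentence of SAP section 6.3.2 treats non-rejection as support for proportionality, and it is easier to satisfy as the data become noisier or the dose range shrinks. The practical importance depends on the unknown CV: negligible at 20% for departures of 1.58-fold or more, and material from moderate CVs upward (48% for a 1.58-fold and 19% for a 2.0-fold departure at CV 50%). These figures rest on the assumed CVs, the planned doses and full evaluability. The effect is confined to a descriptive pharmacokinetic statement; on these documents, neither the escalation criteria nor the primary safety results depend on it. The sentence should be changed because it is wrong as written and cheap to correct.

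**What to change.** Delete the closing sentence of SAP section 6.3.2 and put in its place:

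> For Cmax and AUC0-t the slope will be reported with its 90% CI, together with the implied fold-departure in dose-normalised exposure, r^(slope − 1), and its 90% CI, where r is the ratio of the highest to the lowest dose actually studied. A CI that includes 1 does not by itself establish dose proportionality.

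In the last sentence, the CI meant is that of the slope. Defining r by the doses actually studied is needed because the planned levels may change. The fold scale shows the reader directly what the interval leaves open.

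I would not add an acceptance margin. As an illustration with limits that are not in the documents, requiring the fold-departure to lie within 0.80–1.25 over a 10-fold range means the whole slope CI must lie within 0.903–1.097 (1 + ln 0.8/ln 10 and 1 + ln 1.25/ln 10). Under exact proportionality, 24 active subjects would achieve that only about 25% of the time at CV 20% and about 1% at CV 30%.

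The cost is SAP wording only. The model, data and CI are already planned, and the fold-departure is a transformation of the slope. The downside is that the report may make no yes/no statement on proportionality, and the section will still not set a formal weight for CI width.

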6.4 Safety

All safety analysis reporting will be based on the Safety Population.

6.4.1 Adverse Events

An adverse event (AE) is recorded if it is a new event that was not present at Screening, or is the worsening of an event present at Screening. A treatment-emergent adverse event (TEAE) is defined as any AE that starts or worsens after first dose of study drug. Partial start dates will be imputed according to Appendix 1 for the determination of treatment-emergence. Any AEs with missing start time that occur or worsen on study day 1 will be assumed to be treatment-emergent.

AEs will also be assessed for outcome, severity, relationship to study drug, and seriousness. Any missing severity assessments will be assumed to be Grade 3 (severe) and missing relationship assessments will be assumed to be related. Expected AEs related to KNX100 treatment are provided in the KNX100 Investigator's Brochure. Adverse events will be coded based on the MedDRA for reporting by SOC and PT. SOC's will be ordered in accordance with the international agreed upon sort order for SOC followed by descending order of overall incidence. The MedDRA version used for reporting will be described in the relevant table and listing footnotes.

An overview of TEAEs will be produced, including counts and percentages of subjects as well as number of events by study part and cohort with any incidences of: TEAEs, TEAEs grade 3 or higher, TESAEs, TEAEs related to study treatment, and TESAEs related to study treatment.

Summaries of adverse events by SOC and PT will present the number and percentage of total subjects and number of events (where noted below) by study part and cohort and will include the following types:

- TEAEs (including number of events)

- TEAEs by maximum severity
- TEAEs by highest relationship to study treatment
- Treatment-emergent SAEs

When calculating the incidence of AEs, each AE will be counted only once for a given subject within a MedDRA category (e.g., overall, system organ class, or preferred term), but all occurrences of the same event will be counted in the number of events. When AEs are summarized within levels of another AE assessment (e.g., relatedness or severity), AEs will be counted once per subject at the worst/highest level of the assessment (e.g., highest relationship to study drug or greatest severity).

A comprehensive listing of all adverse events will be provided in a by-subject data listing. In addition, a listing of all treatment-emergent SAEs will be provided.

6.4.2 Clinical Laboratory Evaluations

Serum chemistry, hematology, coagulation, and urinalysis parameters reported as numeric values will be summarized based on SI units. The following laboratory tests will be included in data summaries:

- Serum chemistry: Alanine Aminotransferase (ALT), Albumin, Alkaline Phosphatase (ALP), Aspartate Aminotransferase (AST), Bicarbonate, Bilirubin, Urea, Calcium, Chloride, Creatinine, Gamma-Glutamyl Transferase, Glucose, Lactate Dehydrogenase, Phosphate, Potassium, Protein, Sodium
- Hematology: Hematocrit, Hemoglobin, Mean Corpuscular Volume, Platelets, Erythrocytes, Leukocytes, Basophils, Basophils/Leukocytes, Eosinophils, Eosinophils/Leukocytes, Lymphocytes, Lymphocytes/Leukocytes, Monocytes, Monocytes/Leukocytes, Neutrophils, Neutrophils/Leukocytes
- Coagulation: Activated Partial Thromboplastin Time, Prothrombin Time
- Urinalysis: Bilirubin, Blood, Glucose, Ketones, Leukocytes, Nitrite, PH, Protein, Specific Gravity, Urobilinogen
- Thyroid function tests: Thyroxine, Free; Triiodothyronine, Free; Thyroid Stimulating Hormone

Observed values and changes from baseline for laboratory evaluations will be summarized by study part and cohort at each visit/timepoint as well as minimum and maximum post-baseline. Serum chemistry and hematology will also be summarized in shift from baseline tables by visit/timepoint and normal reference range (low, normal, high).

Liver function tests using various thresholds above the upper limit of normal will be summarized, including any subjects meeting the criteria for potential Hy's Law defined as (AST \geq 3 x ULN or ALT \geq 3 x ULN) and (Total Bilirubin > 2 x ULN) and (ALP < 2 x ULN) at the same visit.

Potentially clinically significant post-baseline thyroid function test results will be summarized by study part and cohort at each visit.

Thyroid Function Test	Criteria
Triiodothyronine, Free [T3]	< 3.5 pmol/L

Thyroid Function Test	Criteria
	> 7.2 pmol/L
Thyroxine, Free [T4]	< 9 pmol/L > 25 pmol/L
Thyroid Stimulating Hormone	< 0.4 mIU/L > 4.0 mIU/L

All laboratory parameters will be provided in by-subject data listings and values that are outside normal ranges (high vs. low; normal vs. abnormal) will be flagged. Serum chemistry, hematology, coagulation, urinalysis, and viral serology laboratory parameters with results determined by the investigator to be clinically significant will also be listed by subject and visit.

6.4.3 Vital Signs

Vital signs and body measurements include: height (cm); weight (kg); BMI (kg/m²); systolic and diastolic blood pressure (mmHg); heart rate (beats/min); respiratory rate (breaths/min); oxygen saturation (%); temperature (°C); and the highest of 3 peak flow measurements (L/min) taken on Day 1 will be recorded on the CRF. Observed values and changes from baseline for vital signs will be summarized by study part and cohort at each visit and time point.

Potentially clinically significant post-baseline results will be summarized by study part and cohort at each visit and timepoint.

Vital Sign	Criteria
Systolic BP	> 150 mmHg > 200 mmHg ≤ 80 mmHg
Diastolic BP	> 100 mmHg > 110 mmHg
Heart Rate	< 50 bpm > 120 bpm ≥ 30 bpm increase from baseline ≥ 30 bpm decrease from baseline
Respiratory Rate	< 8 breaths/min > 24 breaths/min
Oxygen Saturation	< 95%
Temperature	> 38.3°C increase of ≥ 1.1°C from baseline

All vital signs results will be provided in by-subject data listings.

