6.21. Removal of Subjects from the Study or Study Drug

6.21.1. Criteria for Discontinuation or Withdrawal of a Subject

The primary reason for discontinuation or withdrawal of the subject from the study should be recorded in the eCRF, using the following categories:

- Voluntary withdrawal by subject decision
 - The subject is at any time free to withdraw his or her participation in the study, without prejudice and independent of any decision concerning participation in other aspects of this study.
- AE
 - The subject has experienced an AE that requires early termination because continued participation imposes an unacceptable risk to the subject's health, or the subject is unwilling to continue because of the AE.
- Vital signs
 - Measurement of abnormal and out of range parameters on repeat analysis as required (postdose):
 - O₂ saturation of <90% for 60 seconds or longer
 - Respiratory rate of <8 breaths/minute for 2 or more minutes
 - Heart rate of <50 bpm
 - Systolic blood pressure of ≤80 mmHg
 - Temperature of ≤32°C
- EEG
 - Evidence of the emergence of epileptiform discharges as evaluated by an epileptologist or a Level 3 ANZAN certified neurologist.
- ECG
 - QTcF duration >475 ms and increase exceeding 40 ms in males
 - QTcF duration >475 ms and increase exceeding 60 ms in females
- Thyroid function tests outside the normal reference ranges (and upon repeat) and CTCAE Grade 2 or above. That is, symptomatic and requiring treatment.
- Laboratory Parameters
 - Safety laboratory tests that are outside the normal reference ranges (and upon repeat) and deemed clinically significant by the study PI.

- Pretreatment event
 - The subject has a pretreatment event that requires early termination because continued participation imposes an unacceptable risk, or the subject is unwilling to continue due to the pretreatment event.
- Pregnancy
 - If the subject is found to be pregnant, the subject must be withdrawn immediately.
- Major protocol deviation as judged by the investigator and/or Kinosis.
 - The discovery post-randomization that the subject was incorrectly initiated on investigational drug, failed to meet protocol entry criteria, or did not adhere to protocol requirements **and** continued participation poses an unacceptable risk to the subject's health.
- Compliance
 - The subject has poor compliance with study drug or study procedures.
- Additional treatment

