 - The subject requires treatment with another drug that will interfere with evaluation of the study drug.

Subjects that are withdrawn from the study but are evaluable will not be replaced. Any subject that is withdrawn and is not evaluable will be replaced to ensure a minimum number of evaluable subjects.

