5.3 Data Imputation Rules

Generally, missing data will not be imputed, and will be presented as collected in the study database.

In cases where adverse event or medication dates are missing, the imputation methods described in Appendix 1 will be used to determine flags for treatment-emergent events and concomitant medications.

Other missing data methods will be described within the respective analysis section, as appropriate.

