6.4.5 Electrocardiogram (ECG)

Electrocardiogram (ECG) parameters include: HR (beats/min), PR interval (msec), RR interval (msec), QRS duration (msec), QT interval (msec), QTcB interval (msec), QTcF interval (msec), P wave (msec), and T wave (msec). Observed values and changes from baseline for ECG parameters

will be summarized by study part and cohort at each visit and time point. If triplicate reads are taken, the mean of the reads will serve as the observed value at the specific visit and timepoint.

Investigator-reported ECG findings shifts from baseline to each post-baseline visit/timepoint and maximum post-baseline will be summarized by study part and cohort. Categories of Normal, Abnormal – Not Clinically Significant, and Abnormal – Clinically Significant will be included.

Subjects meeting the following potentially clinically significant criteria post-baseline will also be presented:

- 450 msec < QTcF / QTcB ≤ 480 msec
- 480 msec < QTcF / QTcB ≤ 500 msec
- 500 msec < QTcF / QTcB
- 30 msec < QTcF / QTcB change from baseline ≤ 60 msec
- 60 msec < QTcF / QTcB change from baseline

All ECG parameter results will be provided in by-subject data listings.

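### In Part B, vital signs are tabulated only visit by visit, so later-day means omit subjects withdrawn on the same measures, and no table counts subjects who ever met a significance criterion

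*SAP*

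**What the plan says.** Protocol 8.5.1 and SAP section 2 make change from baseline in vital signs and ECGs a primary safety endpoint.

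- **Vital signs (SAP 6.4.3).** "Observed values and changes from baseline for vital signs will be summarized by study part and cohort at each visit and time point". The PCS counts are also given per visit and timepoint. No minimum, maximum or any-post-baseline summary is defined.
- **ECG (SAP 6.4.5).** "Observed values and changes from baseline for ECG parameters" are summarised the same way. This section also presents subjects meeting QTc criteria at any time post-baseline, and a maximum post-baseline shift of the investigator's overall reading.
- **Missing data (SAP 5.3).** "Generally, missing data will not be imputed, and will be presented as collected in the study database".
- **Other safety data.** Laboratory results are summarised "at each visit/timepoint as well as minimum and maximum post-baseline" (SAP 6.4.2). Gastrointestinal symptoms have an any-post-baseline count (SAP 6.4.7).
- **Unscheduled and multiple readings (SAP 5.4).** Unscheduled data may enter minimum/maximum and PCS-incidence summaries. Where one timepoint has several values, the later one is analysed.
- **Withdrawal (Protocol 6.21.1).** The post-dose vital-sign criteria include "Heart rate of <50 bpm", with limits for low systolic pressure, respiratory rate, saturation and temperature. Protocol 9.9 counts failure to withdraw a subject who met the criteria as a violation.
- **Replacement (Protocol 6.21.1).** "Any subject that is withdrawn and is not evaluable will be replaced to ensure a minimum number of evaluable subjects". Protocol 5.3.4 requires an evaluable subject to have completed all assessments.

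**The concern.** Part B doses for seven days. A subject withdrawn on Day 2 for a low heart rate has no on-treatment reading on Days 3 to 7, and the reason is the outcome being summarised. Each later mean then describes subjects who had not reached a limit, whereas the objective concerns everyone treated. A replacement who reaches Day 7 has also not been withdrawn, so replacement does not correct the mean.

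The threshold counts have a separate weakness. Rows per timepoint cannot be added up to a number of subjects: one case at each of two timepoints may be one subject or two. For a tolerability objective with six active subjects per cohort, the number who ever met a criterion is the natural summary, and it is missing for vital signs.

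**Working it through.** The study is descriptive. The documents give no SD, effect size or withdrawal rate, so there is no planned figure to reproduce. The heart-rate and QTcF sizes below are illustrations on assumed values.

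**1. Withdrawal limits against the 6.4.3 table.** The PCS rows match the withdrawal limits for heart rate, systolic pressure and respiratory rate. The saturation row (<95%) takes in the <90% limit. Temperature has rows for high values and rises only, so the ≤32°C limit has no row.

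**2. Why heart rate matters most.** Protocol 4.3 (exclusion 3) admits pulse rates down to 50 bpm, and 6.21.1 withdraws below 50 bpm. A subject entering near 50 needs only a small fall to qualify.

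**3. Arithmetic for one withdrawal among six active subjects.** Mean over all six = (d + 5m)/6, where d is the withdrawn subject's change and m the mean change of the other five. Later visits show m. With m = −2 bpm:

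| d (bpm) | Mean of six | Shown later | Gap |
|---|---|---|---|
| −15 | −25/6 = −4.2 | −2 | 2.2 |
| −20 | −30/6 = −5.0 | −2 | 3.0 |
| −25 | −35/6 = −5.8 | −2 | 3.8 |

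This assumes that the change would have persisted.

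**4. Average over many subjects.** Simulation of seven daily readings. Assumptions: resting rate mean 65, SD 9, entry range 50–90; within-subject SD 4; an individual drug effect constant over days; withdrawal when a reading and its repeat (SD 2) are both below 50. Bias is the Day 7 mean change in retained subjects minus that in all subjects. Cells show bias in bpm and, in brackets, the share withdrawn before Day 7.

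| True mean effect | Effect SD 3 | Effect SD 6 | Effect SD 9 |
|---|---|---|---|
| 0 | 0.13 (2.6%) | 0.58 (6.2%) | 1.48 (10.5%) |
| −3 | 0.28 (7.3%) | 0.94 (11.3%) | 2.09 (16.0%) |
| −6 | 0.45 (14.9%) | 1.38 (18.7%) | 2.82 (23.0%) |
| −10 | 0.70 (29.6%) | 2.06 (31.8%) | 3.95 (34.3%) |

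The chance that at least one of six is withdrawn is 1 − (1 − p)^6, where p is the share withdrawn: 0.15 at p = 2.6% and 0.92 at p = 34.3%.

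**5. The same check for QTcF.** Assumed baseline 405 ms, SD 18, within-subject SD 7, effect SD 5 or 15, male limit. Understatement is under 0.1 ms at no mean effect, and at most 0.3, 0.8 and 1.8 ms at mean effects of +10, +20 and +30 ms. The share withdrawn is 0% to 8%.

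**6. Denominator.** A Part B subject withdrawn mid-course has not completed all assessments, so is not evaluable and is replaced. The Safety Set keeps both subjects. One PCS subject is then 1/7 = 14%, not 1/6 = 17%. SAP 5.1 allows either the cohort number or the non-missing number as denominator, so the rate is not fixed.

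**7. Repeat readings.** Protocol 6.5 has out-of-range vital signs repeated. If the repeat is stored under the same timepoint, SAP 5.4 analyses the repeat only. A first reading below 50 bpm followed by one at 50 or above then leaves both the mean and the PCS count.

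**The case against.** Much is already in place. SAP 5.1 keeps all data up to withdrawal, so the triggering value stays in the analysis and, except for low temperature, has a PCS row to fall in. Protocol 6.17.9 makes an abnormal finding reportable as an adverse event when it leads to treatment discontinuation, and SAP 6.4.1 counts each event once per subject. Discontinuation reasons are tabulated by cohort (SAP 6.1.1), every value is listed, and withdrawn subjects attend the end-of-study visit. Dose escalation does not rest on these tables, because Protocol 5.3.4 has the review committee see each subject's vital signs.

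All of that stands, and it limits the consequence without filling the gap. Adverse-event tables do not count subjects who met a PCS criterion that was neither reported as an event nor led to withdrawal. They also include no summary of events leading to discontinuation, although that is a listed endpoint. The end-of-study visit is off treatment. SAP 5.4 permits unscheduled data in minimum/maximum and PCS-incidence summaries, but 6.4.3 defines neither summary for vital signs.

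Four stronger inferences are tempting, and the documents do not support them:

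- **That a QTcF withdrawal would be hidden.** A QTcF above 475 ms with a rise above 40 or 60 ms falls within the per-subject post-baseline categories of SAP 6.4.5.
- **That replacement conceals the loss.** With both subjects in the Safety Set, the table shows N = 7 against n = 6.
- **That the bias always flatters the drug.** The vital-sign limits concern low values only; losing low-heart-rate subjects would not hide a rise in heart rate.
- **That QTcF means are distorted by a large fraction.** This requires assuming a withdrawal in a cohort of six; the averaged effect in step 5 is small.

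**Conclusion.** The point holds as a gap in SAP 6.4.3, mainly for Part B. Later-day vital-sign means can understate change in the direction of the withdrawal limits, and no table reports how many treated subjects ever met a PCS criterion. For heart rate the illustrative bias is 0.1 to 4.0 bpm. It depends wholly on the assumed SDs and effects, and on withdrawal being applied whenever a repeat confirms the limit. Protocol 6.5 leaves some repeat-abnormal readings to the investigator's discretion, so actual withdrawals, and the bias, could be fewer and smaller.

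The ECG part is minor: only the numeric intervals lack a minimum and maximum. Part A is little affected, because withdrawal after a single dose cannot change exposure and few later timepoints remain. The change is worth making before database lock because the SAP already uses the better summaries for laboratory and gastrointestinal data.

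**What to change.** 1. In SAP 6.4.3, add minimum and maximum post-baseline value and change for each vital sign, and an any-post-baseline row for each PCS criterion. Use all Safety Set subjects, withdrawn and replacement alike, as the denominator. State that unscheduled, repeat and at-withdrawal readings are included.
2. Add a low-temperature row, or state that the post-baseline minimum serves that purpose.
3. In SAP 6.4.5, add minimum and maximum for the numeric ECG intervals, for consistency.
4. Footnote per-visit means with the numbers withdrawn and replaced before that visit.
5. Reconcile the passages that decide who is missing: the discretion in Protocol 6.5 with 6.21.1 and 9.9, and the unqualified replacement of discontinued subjects in 3.1 with the evaluability condition in 6.21.1.

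Items 1 to 4 cost SAP wording and a few table rows from data already collected; item 5 is a clarification of the protocol text. The downside is that worst values become more extreme as readings accumulate, so they should be read against pooled placebo of the same part. Cohort 3 is measured after each of two daily doses, which makes even that comparison slightly uneven.
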